[figure not shown]

**SEGA - SEdation versus General Anesthesia for Endovascular Therapy in Acute Ischemic Stroke
– a Randomized Comparative Effectiveness Trial.**

NCT03263117

Version Date: 05/10/2022

SEGA CLINICAL TRIAL PROTOCOL

PROTOCOL NUMBER	HSC-MS-17-0436	
PROTOCOL TITLE	SEGA - SEdation versus General Anesthesia for Endovascular Therapy in Acute Ischemic Stroke – a Randomized Comparative Effectiveness Trial.	
VERSION / DATE	5.0 May 4, 2022	
AMENDMENTS / DATE	- / -	
SPONSOR	McGovern Medical School at The University of Texas Health Science Center at Houston (UTHealth), Department of Neurosurgery (Weatherhead Foundation)	
STEERING COMMITTEE	STUDY CHAIR [name] [name] Associate [name] of Neurosurgery McGovern Medical School at UTHealth  	STUDY Co-CHAIR [name] MS Associate [name] of Neurology McGovern Medical School at UTHealth
	STUDY Co-CHAIR [name] Associate [name] of Anesthesiology McGovern Medical School at UTHealth  	UTH SITE PI [name] Assistant [name] of Neurology McGovern Medical School at UTHealth
	STATISTICIAN [name] Associate [name] for Clinical Research and Evidence-Based Medicine, McGovern Medical School at UT Health  	COMMITTEE MEMBER [name] [name] of Neurology McGovern Medical School at UTHealth [name]

IRB NUMBER: HSC-MS 17-0436

PROTOCOL SYNOPSIS

Title	SEGA: Sedation versus General Anesthesia for Endovascular Therapy in Acute Ischemic Stroke – a Randomized Comparative Effectiveness Trial.
Study Purpose	
Background: Endovascular therapy (EVT) with stent retrievers improve functional outcome in acute stroke patients. Although both are routinely performed as usual care during EVT, controversy remains regarding the optimal type of anesthesia during EVT – general anesthesia (GA) vs. sedation (CS). Retrospective case-control studies found an association between better clinical outcomes with the latter. However, one small, single-center randomized trial suggested no significant differences in early outcomes.
 
Primary Objective: To estimate overall treatment benefit (improvement in disability) among acute ischemic stroke patients that are randomized to GA compared with CS during endovascular therapy.
 
Secondary Objectives: Assess safety (as measured by incidence of symptomatic intracranial hemorrhage); rates of EVT procedural complications, reperfusion; and quality of life.

Design	Multicenter, randomized, comparative effectiveness trial with un-blinded caregivers but blinded assessors (PROBE – Prospective Randomized Outcome Blinded Endpoint).
Study Population Overview	260 total acute ischemic stroke patients with proximal intracranial arterial occlusions treated with endovascular therapy within 16 hours of symptom onset. Patients must not require intubation for any clinical indication. Arterial occlusion must be demonstrated by either CT-angiogram (CTA) or MR-angiogram (MRA).
Intervention	
Time of randomization is study time=0. Patients will be randomized 1:1 to receive during endovascular therapy either:
 
 1) General anesthesia (balanced for equal randomization into intravenous vs. inhalational) or 2) Sedation 
Both GA and CS delivered and managed by anesthesiologist.

Primary Outcome	Independent functional outcome as measured by the modified ordinal Rankin Scale (mRS) at 90 days assessed by study personnel blinded to treatment.
Secondary Outcomes	
 1) Dichotomized mRS at 90 days (0-2 vs 3-6) 2) Safety as measured by rates of symptomatic intracerebral hemorrhage within 24-36 hours after endovascular therapy. 3) Angiographic reperfusion defined as modified TICI score $\geq 2b$. 4) Peri-procedural complications. 5) Difference in 24-36-hour NIHSS scale. 6) Proportion of independent functional outcome at 90 days in GA patients treated with inhalational vs. intravenous medications. 7) Difference in quality of life at 90-days.

IRB NUMBER: HSC-MS-17-043

Study Duration	
Total trial duration: 24 ± 4 months
 
 
Enrollment – approximately 18 months with 6 months of data-monitoring and statistical analysis 
Patient participation - 90 days
Statistics	
 
Planned number of sites (US + international): 10-15. 
Sample size: 260 patients randomized 1:1 (130 per group). 
Final analysis uses a Bayesian approach to obtain odds ratio (OR) of good functional outcome at 90-days. Bayesian prior assumes treatment equipoise and uses a neutral, informative prior (OR=1.0; 95% credible intervals of 0.3-3.0). 
Trial success is defined as a >80% posterior probability that GA is superior (OR >1.0 of 90-day mRS) to CS.

10.1 DATA COLLECTION	22
11.0 STUDY COMMITTEES AND CORE LABS	23
11.1 STEERING COMMITTEE	23
11.2 DATA SAFETY MONITORING COMMITTEE	23
11.3 IMAGING CORE LABS	23
12.0 REFERENCES	25
13.0 APPENDICES	27
APPENDIX I. RICHMOND AGITATION SEDATION SCALE (RASS)	28
APPENDIX II. MONTE CARLO SIMULATION RESULTS OF BAYESIAN POWER	29
APPENDIX III NPO GUIDELINES	29

IRB NUMBER: HSC-MS-17-0436

List of Abbreviations

A1	1 st segment of anterior cerebral artery
A2	2 nd segment of anterior cerebral artery
ACA	Anterior Cerebral Artery
AE	Adverse event
AHA	American Heart Association
A-line or Aline	Arterial Line
ASA	American Stroke Association
aICH	Asymptomatic intracerebral hemorrhage
aPTT	Activated partial thromboplastin time
aOR	Adjusted Odds Ratio
aRR	Adjusted Relative Risk
ASPECTS	Alberta Stroke Program Early CT Score
BA	Basilar Artery
BP	Blood Pressure
CABG	Coronary artery bypass graft
CAS	Carotid Artery Stenting
CBC	Complete blood count
CEA	Carotid Endarterectomy
CFR	Code of Federal Regulations
CI	Confidence interval
CK	Creatine kinase
CrCl	Creatinine clearance
CrI	Credible Interval
CO ₂	Carbon dioxide
CRF	Case Report Form
CS	Conscious Sedation
CT	Computed tomography
CTA	Computed tomography-Angiogram
CTP	Computed tomography-Perfusion
CVA	Cerebrovascular accident
DBP	Diastolic blood pressure
DTN	Door to needle
DTG	Door to groin
ECG	Electrocardiogram
EDH	Epidural Hematoma
eGFR	Estimated Glomerular Filtration Rate
ESCAPE	Endovascular Treatment for Small Core and Proximal Occlusion Ischemic Stroke
EQ-5D	European Quality of Life-5 Dimensions
EVT or ET	Endovascular Therapy
EXTEND-IA	Extending the Time for Thrombolysis in Emergency Neurological Deficits - Intra-Arterial
GA	General Anesthesia
GI	Gastrointestinal
H, h or hr, hrs	Hour(s)
βHCG	beta-human chorionic gonadotropin
HERMES	Highly EffectiveReperfusion evaluated in Multiple Endovascular Stroke
HT1 or HT-1	Hemorrhagic Transformation Type-1
HT2 or HT-2	Hemorrhagic Transformation Type-2
ICA	Internal carotid artery

ICH	Intracranial hemorrhage
IRB	Institutional Review Board
IV	Intravenous
IV-tPA	Intravenous recombinant tissue plasminogen activator
IVH	Intraventricular Hemorrhage
kg	Kilogram
LFT	Liver function test
LMWH	Low molecular weight heparin
LOS	Length of stay
M1	1 st segment of middle cerebral artery
M2	2 nd segment of middle cerebral artery
M3	3 rd segment of middle cerebral artery
mmHg	Millimeters of mercury
MAP	Mean arterial pressure
MCA	Middle cerebral artery
MR CLEAN	Multicenter Randomized Clinical trial of Endovascular Treatment in the Netherlands
mRS	Modified Rankin Scale
mTICI	Modified Thrombolysis In Cerebral Ischemia
NA	Not available or Not applicable
ND	Not done
NIHSS	National Institute of Health Stroke Scale
NNH	Number needed to harm
NNT	Number needed to treat
OR	Odds Ratio
pH	Hydrogen ion concentration
PH1 or PH-1	Parenchymal Hematoma Type-1
PH2 or PH-2	Parenchymal Hematoma Type-2
Q or q	Every
rt-PA or tPA	Recombinant tissue plasminogen activator
RCT	Randomized Clinical Trial
REVASCAT	Endovascular Revascularization With Solitaire Device Versus Best Medical Therapy in Anterior Circulation Stroke Within 8 Hours
SAE	Serious adverse event
SAH	Subarachnoid hemorrhage
SBP	Systolic blood pressure
SD	Standard deviation
SDH	Subdural Hematoma
sICH	Symptomatic Intracerebral Hemorrhage
SIESTA	Sedation vs. intubation for endovascular stroke treatment
SWIFT-PRIME	Solitaire with the intention for thrombectomy as primary endovascular treatment trial
tICA or TICA	Terminal Internal Carotid Artery
TICI	Thrombolysis In Cerebral Ischemia
TNKase	Tenecteplase
VA	Vertebral artery

1.0 BACKGROUND AND RATIONALE

Stroke is the fourth leading cause of death in developed nations. Each year in the US, approximately 795,000 people experience a new or recurrent stroke. On average, every 40 seconds, someone in the United States has a stroke.¹ Representing approximately 30-40% of all ischemic strokes, proximal intracranial arterial occlusions result in the most disabling types of ischemic strokes, and are closely associated with poor neurological outcomes at hospital discharge.² Recent randomized clinical trials conclusively demonstrated that early endovascular therapy (EVT) with stent-retrievers (i.e., embolectomy) significantly improves functional outcomes in patients with acute ischemic stroke up to 6 hours after onset and are recommended by the American Heart Association/Stroke Association (AHA/ASA).³⁻⁶ However, controversy remains regarding the optimal type of anesthesia that should be used during in EVT.⁷⁻¹⁰ The AHA/ASA guidelines do not support a recommended choice of anesthesia as the selection should be individualized to the patient (Class IIb; Level of Evidence C).¹¹ Further, the guidelines state that randomized trials are needed.

1.1 Retrospective Studies of Anesthesia during Endovascular Therapy

Many retrospective case-control studies, propensity score analyses and post-hoc analyses of EVT trials have suggested, compared to CS, an association between GA and worse stroke outcomes including mortality – see table 1.¹²⁻¹⁹ In these studies, GA compared to conscious sedation (CS) in EVT reduced the odds of 90-day good functional outcome (mRS \leq 2).

Following 1:1 matching using propensity score analysis, 507 general anesthesia and 507 CS patients, the outcome of thrombectomy patients receiving CS had decreased in-hospital mortality, pneumonia, and lower hospital costs and lengths of stay when compared with patients who received general anesthesia.¹² This study suffered significant selection bias, which compromised its conclusion. A post-hoc analysis of the thrombectomy patients in MR CLEAN (Multicenter Randomized Clinical trial of Endovascular Treatment in the Netherlands) showed better functional 90-day outcome in the absence of general anesthesia, but again, patients were not randomized to the type of anesthesia.¹⁷

1.2 Randomized Trials of conscious sedation vs. general anesthesia during Endovascular Therapy

Until the recent publication of the first randomized trial testing general anesthesia vs. CS,²⁰ none of these studies randomized patients to a particular anesthesia approach – see table 1. The SIESTA trial randomized 150 (1:1) EVT treated stroke patients to either GA or CS at a single institution in Germany. The primary outcome, improvements in 24-hour mean NIHSS scores were nearly identical (3.2 vs. 3.6 points in GA vs. CS, respectively). The mean difference between the two groups was 0.4 and not statistically significant, P=0.82. Both arms demonstrated similar rates of successful angiographic reperfusion (TICI 2b or 3): 89%-GA vs. 81%-CS. More GA patients had prolonged intubation, incidence of pneumonia and hypothermia. Despite the increased incidence of adverse events and lack of clinical improvement at 24 hours, GA patients were more likely to be functionally independent (mRS \leq 2) at 90 days: 37% GA vs. 18% CS, P=0.01 (see table 1). Both in-hospital and 90-day mortality were nearly identical in the two study arms. Authors concluded SIESTA results did not support superiority of CS over GA and they recommended a larger, multicenter RCT powered to address longer-term outcomes.

Table 1. Summary of clinical studies of ET and anesthesia. Shaded row indicates the lone RCT of EVT patients randomized to GA versus CS.

REF	Design	Anesthesia Preferred	Benefit	Harm	Comments
12	Retrospective Propensity Analysis	Sedation	
 Sedation associated with: 
 ↓ hospital mortality; ↓ pneumonia; ↓ hospital costs/LOS 	GA associated with: 
 ↑ in-hospital mortality (25% v 12%) OR=2.4, 95%CI 1.7-3.4, p<0.001. ↑ pneumonia 17% v 9% OR=2, 95%CI 1.4-2.96, p<0.001. • ICH/SAH rates similar: 11% v 12%, p=0.62. 	
 - 1:1 propensity score matching 507 GA & 507 CS patients - Usage rate of GA decreased from 83.8% in 2006 to 74% in 2013.
13	Post-Hoc analysis of Multicenter RCT (IMS-3)	Sedation	No significant difference in: 
 - Adjusted risk of SAH (P=0.32) or sICH P=0.37 	
 • GA associated with: 
 ↑ in-hospital mortality - aRR 2.8; 95%CI, 1.7-4.9, P<0.001 • ↓ 90d mRS ≤2, RR 0.68; 95%CI 0.5-0.9; P=0.006 	
 Sedation – 269 (62%) GA – 147 (33.9%) Undetermined – 18 (4%)
14	Retrospective analysis (n=126)	Sedation	
 • Intra-procedural complications lower in patients who received Sedation 6% v GA 15% P=0.13 • Sedation assoc with good outcome (OR 3.06, P=0.04) 	GA associated with ↑ICU LOS: 6.5 days v 3.2 days, P<0.001	Sedation – 73 (58%); GA – 53 (42%)
15	Retrospective analysis (n=109)	Sedation	Duration of procedure & time to revascularization was significantly lower in Sedation	GA 18% greater mortality rate compared with the CS group (P=0.045)	
 - CS – 74; GA - 35 - GA & post procedure glucose significant predictors of mortality
16	Retrospective pre-trial Cohort of MR-CLEAN (n=348)	Sedation	
 • Sedation better clinical outcomes - (OR 2.1, 95% CI, 1.02–4.31) • After adjusting for pre-specified prognostic factors, statistical significance was lost (OR1.9, 95% CI, 0.89–4.24). 	
 No difference in sICH or Asymptomatic ICH Mortality - GA group (21%) vs. Sedation (17%) No difference in device dissection or device-related complications 	CS - 278 GA - 70
17	Post-Hoc analysis of RCT (MR-CLEAN)	Sedation	mRS in favor of non-GA compared to control group (adjusted common OR 2.2, 95%CI 1.5-3.2.	GA associated with significant (p = 0.011) effect modification, resulting in estimated ↓ of 51% (95%CI 31%-86%) in EVT effect compared to CS.	Treatment without GA was associated with a significant treatment benefit in MR CLEAN.
18	Retrospective Case-Control	Sedation	
 • No difference in hemorrhage 	GA associated with ↑mRS >2 at 90 days (OR 2.33) and also ↑mortality (OR 1.7)	Older study (2005 – 2009); n=980
19	Post-Hoc Meta-Analysis of 9 studies	Sedation	
 • No difference in treatment times between the two groups 	GA associated with: 
 ↑mortality OR 2.6, ↑respiratory complications OR 2.1 ↓good clinical outcomes (OR = 0.43) 	
 - GA patients with higher NIHSS presenting scores. - n=1956
20	RCT Monocentric	GA - no support for CS advantage	
 • No significant difference (P=0.82) in primary outcome (24 hour NIHSS) between groups. • ↑ mRS ≤2 at 90d 37%-GA v. 18% CS without mortality diff. 	
 GA had more: 
 - hypothermia (32%, P<0.001) - delayed extubation (49.3%, P<0.001) - pneumonia (13.7%, P=0.03) 	Only RCT that randomized EVT patients to either GA or CS. Sedation – 77; GA - 73
Campbell (ISC 2017)	Post-Hoc Meta-Analysis 5 RCTs	Sedation	
 • Both CS & GA superior compared to usual care • Equivalent procedure complications 	
 ↑good outcomes in non-GA group (OR 1.6). ↑ pneumonia in GA group (16% v 9%), - Randomization to treatment time prolonged in GA 	HERMES collaboration; n=1287; NIHSS, age, onset to random. times comparable CS v. GA

A recent retrospective study of a multi-hospital administrative database between 2006-2013, found 80% of 2515 EVT patients received GA, whereas 20%, received CS.²¹ These findings suggest the majority of neuro-interventionists preferred GA. Since that time, multiple retrospective studies have been published (detailed in table 1) that suggest CS may be preferable to GA. We recently sent a questionnaire to vascular neurologists and both neurology and neurosurgery trained neuro-interventionalists. The aim was to determine the state of anesthesia equipoise among physicians who perform or direct care for EVT stroke patients. Notably, the questionnaire was sent 4 months after publication of the SIESTA trial. EVT specialists were asked if a randomized trial was still needed – Figure 1. Out of 97 respondents, the responses were similar.

[figure not shown]

Figure 1. Results of questionnaire from comprehensive stroke center's opinion for a current randomized trial of anesthesia in EVT.

For thrombectomy following acute stroke, any delay will likely result further brain infarction. Relative to CS, general anesthesia may result in more delays to recanalization time.⁷ On the other hand, patients who receive CS are more likely to suffer agitation and move while on the treatment table, potentially delaying recanalization as well, and increasing procedural risk. Iatrogenic arterial rupture and inability to catheterize the occluded vessel are key concerns. There has also been speculation of potential anesthetic-related worsening ischemic volume due to a vasodilatory “steal phenomenon”.⁷ The cumulative dose of norepinephrine during general anesthesia was considered a predictor of an unfavorable outcome.²²

GA for EVT can be administered using intravenous anesthetics, inhaled anesthetics, or a combination. There is no clear standard of care as to the type of GA for this procedure: the various retrospective and prospective studies investigating this issue have used both. Lacking evidence of the superiority of one type of anesthetic over the other in EVT, the decision of which type to administer is based on anesthesiologist preference and/or common local practice. Different anesthetic techniques have differential effects on cerebral blood flow, which may affect flow to the penumbra either directly, or by increasing flow to unaffected regions (“steal phenomenon”). One retrospective study found that outcomes were better in patients administered an inhaled general anesthetic compared to intravenous or combination techniques.⁹

As expected secondary to study design, previous retrospective studies comparing the utilization of the CS vs. GA are severely limited by probable selection bias. The “sicker” patients with cardiovascular instability or respiratory distress, agitation, aphasia from dominant hemispheric stroke location, and the inability to protect their airway were typically treated under general anesthesia. These patients remained intubated for the same reasons after the procedure as well; whereas patients who were otherwise conscious and cooperative at baseline, without airway issues, with stable cardiovascular and pulmonary status were selected for EVT under CS. Intuitively, patients within the former group had longer ICU and hospital stay, higher hospital mortality, and worse neurological and functional outcomes. The soundest mechanism for reducing selection bias remains randomization with allocation concealment. Most importantly, randomization balances all the known and unknown patient characteristics. Therefore, a randomized study comparing CS and GA during EVT is needed to evaluate the objective outcomes to help determine the future treatment paradigm.

2.0 STUDY OBJECTIVES

2.1 Primary Objective

To evaluate the hypothesis that GA during EVT for acute ischemic stroke improves functional outcomes at 90 days compared to sedation.

2.2 Secondary Objectives

Evaluate safety, reperfusion, early neurological improvement, effect modification by type of GA, and quality of life in EVT patients randomized to GA versus sedation.

3.0 STUDY ENDPOINTS

3.1 Primary Endpoint

The primary endpoint is a comparison of independent clinical outcome, defined as a modified ordinal Rankin Scale (mRS) at 90 days (scores 5 and 6 combined) among patients randomized to GA versus sedation. Primary analysis will be intention to treat (ITT) and adjusted for stratification variables.

3.2 Secondary Clinical Endpoints

- 1) As treated analysis of primary outcome adjusted for stratification variables
 - a. Patients will be analyzed according to the type of anesthesia received (e.g., a patient randomized to Sedation that crosses-over to GA will be analyzed in the GA group).
- 2) Dichotomized mRS at 90-days (0-2 vs 3-6) adjusted for stratification variables.
- 3) Angiographic reperfusion defined as modified TICI score $\geq 2b$.
- 4) Early clinical improvement measured by difference in 24-36 hour NIHSS scale.
- 5) Proportion of independent functional outcome at 90 days in GA patients treated with inhalational vs. intravenous medications.
- 6) Difference in quality of life at 90-days.

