3.4 Exploratory Analyses

- 1) Ordinal ITT and as-treated analysis of primary outcome comparing three groups (CS, GA IV, GA inhalational) adjusting for stratification variables.
- 2) Multivariable adjusted analysis (including stratification variables) for both primary (mRS 0-2) and ordinal analysis of 90-day mRS outcomes, to include (but not limited to) baseline variables known to be clinically associated with stroke outcomes:
 - a. Age
 - b. NIHSS
 - c. Time from stroke onset-to-EVT groin puncture
 - d. IV-tPA treatment before EVT
 - e. Atrial Fibrillation
- 3) Duration of time during EVT spent below a systolic blood pressure of 140mmHg.
- 4) Total ICU and ventilator days.
- 5) Subgroup analyses to test for heterogeneity in patient benefit and Provider Skill:
 - a. Proximal vs. Distal occlusion location (ICA+M1-MCA vs. others)
 - b. High-volume vs. low-volume centers
- 6) Costs from a health system perspective

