4.2 Enrollment and Randomization

Enrollment in this study is defined as the moment when the randomization process is completed and the subject is assigned to a study arm. After randomization, no crossover is permitted unless either the neurovascular interventionalist or anesthesiologist determines the patient meets criteria as described in section 5.0. Randomization will occur via a secure, password-protected, web-based system. Subjects will be randomized 1:1 to GA or Sedation using permuted blocks and stratified by center, terminal ICA occlusion (yes/no), and time of stroke symptom onset (≤ 6 hours or 6-16 hours). Patients randomized to GA will subsequently be randomly assigned in a 1:1 ratio to either inhalational or IV anesthesia.

Stroke management and endovascular therapy procedures will occur as per local site usual care. Only FDA-approved thrombectomy devices should be used with first line use of stent retriever. Both general anesthesia and Sedation should be delivered and managed by an anesthesiologist.

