9.2 Statistical Analyses

Intent-to-treat analyses will be performed. To summarize the data, descriptive statistics will be used. Demographics, vital signs, laboratory variables, stroke type and duration from onset of symptoms will be summarized for each treatment arm. Vital signs taken during the treatment period will be displayed graphically. In addition to ICH, other medical events will be tabulated by body system and severity.

Primary analyses will focus on comparing GA (combining inhalational and IV anesthesia) to sedation. All analyses will be conducted under a Bayesian paradigm to obtain estimates of odds ratio (OR) for primary outcome (ordinal mRS), relative risk (RR) for binary outcomes, and probability of treatment benefit or harm (quantities that cannot be obtained from frequentist analyses). For the treatment effect, we will use a neutral prior centered at OR of 1.0 with 95% prior interval of 0.3-3.0. This prior assumes a priori equipoise and excludes large treatment effects. Weakly informative priors will be used for all other parameters to exclude large treatment effects.²⁴

Generalized linear mixed models will be used to analyze all outcomes and will include treatment group, terminal ICA occlusion and time from onset of symptoms (stratification variables) as covariates and center (stratification variable) as a random effect to account for center variability. For the primary outcome of ordinal mRS at 3 months (scores 5 and 6 combined), we will use an ordinal logistic model. For binary outcomes we will use log binomial (or logistic in case of non-convergence) models to directly estimate relative risks (or odds ratios) and 95% CIs. The prior for the treatment effect will be a Normal (0, $sd=0.57$) in the log OR/RR scale. The prior for the intercept will be Normal (0, $sd=10$) and Normal (0,1) for other covariates in the model. A half-Normal(0,1) prior will be used for the standard deviation of the center random effect. For non-binary outcomes, we will select the best fitting models and use neutral, weakly informative priors that exclude large treatment effects. We will examine residuals from each model to ensure reasonable adherence to the assumptions of the models.

If, despite randomization with stratification for center, tICA, and time from onset of symptoms, any important differences between intervention groups occur in baseline variables related to outcome, secondary analyses will be performed controlling for these factors.

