For the primary outcome of ordinal mRS at 3 months, a secondary analysis will be conducted comparing CS to inhalational anesthesia and to IV anesthesia adjusting for the stratifying variables. Models and priors will be the same as for the primary analysis.

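### The only named secondary inhalational-versus-intravenous endpoint is a proportion worded by treatment given, although the agent is randomized and the trial's main scale is ordinal

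*Combined protocol and SAP*

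**What the plan says.** Section 4.2 sets up a second randomization: "Patients randomized to GA will subsequently be randomly assigned in a 1:1 ratio to either inhalational or IV anesthesia". With 130 patients in the GA arm, that is about 65 per agent.

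The endpoint for this question, in section 3.2 item 5 and repeated as synopsis secondary outcome 6, is "Proportion of independent functional outcome at 90 days in GA patients treated with inhalational vs. intravenous medications". It states neither an analysis set nor an mRS cut.

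Three other places bear on it:

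- Section 3.4 item 1 lists, as exploratory, "Ordinal ITT and as-treated analysis of primary outcome comparing three groups (CS, GA IV, GA inhalational) adjusting for stratification variables".
- Section 9.2 states that "a secondary analysis will be conducted comparing CS to inhalational anesthesia and to IV anesthesia adjusting for the stratifying variables", on the ordinal scale and with the primary model and priors. Inhalational versus intravenous (IV) is not among the contrasts it names.
- Section 9.2 also opens with a general statement: "Intent-to-treat analyses will be performed".

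The primary endpoint in section 3.1 is "defined as a modified ordinal Rankin Scale (mRS) at 90 days (scores 5 and 6 combined) among patients randomized to GA versus sedation". The only dichotomy that section 3.2 spells out is item 2: "Dichotomized mRS at 90-days (0-2 vs 3-6) adjusted for stratification variables".

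**The concern.** Two features of item 5 fit poorly with the design.

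The first is the grouping. A comparison of randomized agents is protected from selection only if patients are analyzed by the agent assigned. The words *treated with* point to the agent received. Item 1a of the same list moves a sedation patient who crosses over into the GA group for the as-treated analysis, and section 7.1 sends patients who do not tolerate sedation to inhalational GA. If item 5 follows that logic, cross-overs enter one agent group only. They are selected for agitation, airway difficulty, loss of consciousness, aspiration or cardiovascular instability, so their prognosis is plausibly worse.

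The second is the scale. With about 65 patients per agent, reducing six ordered mRS levels to a proportion gives up precision that a small comparison needs.

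The result is that the less precise and ambiguously grouped version has secondary status, while the efficient version by assigned agent is exploratory and not named as a contrast. There is also a difference in status: ordinal comparison of sedation (CS) with each agent is secondary in section 9.2, and the three-group analysis that covers it is exploratory in section 3.4.

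**Working it through.** **Inputs.** From section 9.1: 260 patients, 130 per arm, and a success threshold of Pr(OR>1) > 0.80. From Appendix II: CS rates for mRS 0, 1, 2, 3, 4, 5+6 of 0.10, 0.14, 0.11, 0.19, 0.18, 0.28; OR 1.53 for GA; 10% cross-over from CS to GA. From section 9.2: prior Normal(0, sd 0.57) on the log OR. Assumed: no loss to follow-up and an exact 65/65 split.

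**1. The plan's own figure.** The check used 10,000 simulated trials with a proportional-odds fit, a normal approximation to the posterior, and a CS arm made of 90% CS and 10% GA rates. Covariates and the center effect were left out. At N=260 and threshold 0.80, power is 0.805 against the stated 0.80. At thresholds 0.95, 0.90, 0.85 and 0.75 it is 0.50, 0.65, 0.74 and 0.85 against 0.49, 0.64, 0.73 and 0.85. Type I error at 0.80 is 0.19 against 0.18. The plan's figures reproduce.

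**2. Cross-overs under the literal reading.** 0.10 × 130 = 13 sedation patients receive inhalational GA. The inhalational group becomes 65 + 13 = 78, and 13/78 = 17% of it was never randomized to an agent.

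To illustrate the bias, suppose no true agent difference and the Appendix II rate of 45% with mRS 0-2 under GA. For a cross-over rate r of mRS 0-2, the inhalational proportion is (65 × 0.45 + 13r)/78:

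- r = 0.35 (the plan's CS rate): 33.80/78 = 43.3%, a deficit of 1.7 points
- r = 0.20 (assumed): 31.85/78 = 40.8%, a deficit of 4.2 points
- r = 0.10 (assumed): 30.55/78 = 39.2%, a deficit of 5.8 points

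Analysis by assigned agent avoids this.

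**3. Information lost by the 0-2 split.** At 1:1 allocation, information on the log OR per patient is (1 − Σp³)/12 for the ordinal scale and q(1−q)/4 for the binary one, where q is the proportion with mRS 0-2.

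- CS rates, q = 0.35: 0.0800 and 0.0569; ratio 0.711, loss 28.9%.
- GA rates implied by OR 1.53 (0.145, 0.181, 0.126, 0.191, 0.155, 0.203; q = 0.452): 0.0808 and 0.0619; ratio 0.766, loss 23.4%.
- Average of the two: ratio 0.745, loss 25.5%.

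Both agent groups receive GA, so the second line is the closest match: 130 GA patients analyzed as binary are worth about 130 × 0.766 = 100 analyzed ordinally.

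**4. What section 3.4 item 1 recovers.** In simulated trials of 130 CS, 65 inhalational and 65 IV patients, the inhalational-IV contrast from a three-group ordinal model has a median standard error of 0.310. A direct two-group ordinal fit also gives 0.310.

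**5. Illustrative power, 65 v 65, threshold 0.80 in one direction.** The agent ORs are assumptions.

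| Agent OR | Ordinal | Binary (log OR) |
|---|---|---|
| 1.3 | 0.46 | 0.41 |
| 1.53 | 0.67 | 0.59 |
| 2.0 | 0.90 | 0.84 |

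Section 9.2 specifies relative risks from a log-binomial model for binary outcomes. On that scale, by normal approximation, the comparison is 0.64 v 0.59 at OR 1.5 and 0.90 v 0.86 at OR 2.0. Across ORs of 1.5 to 2.0 the gain is roughly 0.04 to 0.08.

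**The case against.** A reader might infer that the plan contains no ordinal, randomized comparison of the agents and so throws away a quarter of the information. The documents do not support that. Section 3.4 item 1 is ordinal, includes ITT and keeps the two agents separate, and step 4 shows that it yields the contrast at full precision. The loss belongs to item 5 alone. What remains is that the section 3.4 analysis is exploratory, names no pairwise contrast, and is run both ITT and as treated without saying which leads.

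A reader might also infer that item 5 is certainly as treated. That is not established. Section 9.2 states ITT generally, and where the authors want an as-treated analysis (3.2 item 1, 3.4 item 1) they say so. *GA patients* could mean patients randomized to GA, in which case the 13 cross-overs would not enter. The literal reading is likely, but the firm statement is that item 5 leaves its analysis set open.

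Three further limits stand. Section 9.0 refers to a separate statistical analysis plan whose detail is not in the text reviewed, so the contrast may be defined there. The 0-2 cut is borrowed from item 2. The power figures rest on assumed agent effects and on a threshold that the plan sets only for GA over CS; with no direction stated for the agents, the null rate of about 0.17 per direction becomes about 0.34 if either agent may be declared better.

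Finally, a proportion with mRS 0-2 is easy to interpret and is a reasonable secondary measure. That argues for keeping it as supportive. It does not argue for leaving the grouping undefined.

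**Conclusion.** The point holds for the named secondary endpoint and not for the plan as a whole. Item 5 does not say whether patients are grouped by assigned or received agent. Read literally, about 17% of the inhalational group would be non-randomized cross-overs, if 10% of sedation patients cross over and all go to inhalational GA. If the 0-2 cut applies, the endpoint loses about 23% of the ordinal information at the implied GA rates and 29% at the CS rates. The power gain from the ordinal scale is illustrative only, because the documents state no agent effect and no success rule for this comparison. At an agent OR of about 1.5 neither scale reaches 0.80, so the change sharpens the comparison without making it a well-powered one. The primary analysis and the sample size are unaffected.

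**What to change.** - Redefine section 3.2 item 5 and synopsis secondary outcome 6 as the common odds ratio for ordinal 90-day mRS (scores 5 and 6 combined), inhalational versus IV, among patients randomized to GA, by assigned agent (ITT), using the section 9.2 ordinal model and prior.
- Keep the proportion with mRS 0-2 as a supportive measure in the same ITT groups, with the cut stated.
- State that the contrast may be taken from the three-group ordinal ITT model, and name it in sections 3.4 and 9.2.
- Give the CS-versus-each-agent analysis one status, secondary or exploratory, in both sections.
- Label any power figure for the agent comparison as illustrative.

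The cost is wording in four places and one model run on data already collected. If the separate statistical analysis plan already defines the contrast this way, only the protocol wording needs to be aligned with it.
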